#### 10. Risks and Benefits

The risks involved in the study are all small and mild:

- 1. Burns Electrical stimulation can cause burns, although this is very rare with the pulsed current that will be used in this study because electricity is only flowing for a very small proportion of the time with this type of current. The risk of burns is also increased if the electrodes have poor contact with the patients' skin. This will be avoided by closely inspecting the electrodes for good contact when applied, by cleaning the skin with water before applying the electrodes, clipping hair in the area of electrodes if present, and by using new electrodes at least weekly, or sooner if they start to adhere poorly.
- 2. Skin irritation or inflammation the adhesive on electrical stimulation electrodes, which is similar to tape adhesive, can cause skin irritation in some individuals. Therefore, individuals with tape allergy will be excluded from this study. In addition, if a subject develops skin irritation we will switch to hypoallergenic electrodes. If the skin irritation persists, the subject will be withdrawn from the study.
- 3. Discomfort during the stimulation if the intensity is high enough an individual may experience discomfort during electrical stimulation. We will limit the stimulation intensity to that sufficient to produce a visible muscle contraction and will discontinue the intervention if the subject either reports pain or has signs of pain e.g. elevated HR or BP in response to the stimulation.
- 4. Delayed muscle soreness there is a risk of delayed onset muscle soreness in the muscles stimulated. This is similar to the soreness experienced after exercise and will resolve without intervention. This is only likely if the exercise is substantially greater than the individual's usual activity. Although 30 minutes of visible quadriceps contraction is not generally likely to cause delayed onset muscle soreness, it is possible this will occur.
- 5. There is a small risk of breach of confidentiality.

It is hypothesized but unknown whether there are benefits to e-stim treatment. E-stim may result in reduced duration of hospitalization and intubation, and may improve recovery outcomes.

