## f. Consent Process

If a patient meets inclusion criteria, the study team will approach the patient or the legally authorized representative (LAR) for consent. In instances where the patient is unable to give informed consent (brain injury, sedation, etc.), the LAR will be approached for consent. Initial consent discussion will take place in a quiet private place in the Neuro ICU. The written consent form will be presented and reviewed with the patient or the LAR. At this time, the patient or LAR can ask any questions prior to enrollment. Understanding of the study will be assessed after the consent discussion and prior to enrollment by asking pertinent study related questions. When the study staff is satisfied that the patient or LAR understands, the study consent form will be signed. One copy will be given to the patient or patient's LAR, and one copy will be retained by the study team.

In the event that the patient's LAR lives at a distance, the consenting discussion may be conducted by telephone. Prior to this discussion, the LAR will be sent a copy of the consent form by mail, email, or fax. Once the LAR has received the ICF, a member of the study team will contact them by phone and go through the ICF with them, answering any questions that may arise. The LAR will sign their copy of the ICF, and may send it back to the study team by mail, email, or fax.

Version Date 7/22/19

If a patient regains the ability to consent during the study period, the coordinator will return and re-consent the patient him or herself. If the participant during the research study does not wish to continue e-stim treatments, the decision must immediately be respected. Subjects will be asked if they are willing to allow the study staff to perform a brief assessment of their recovery. If so, the subject will be considered to still be enrolled in the study, and it will be noted that the intervention was stopped early. If not, the subject will be considered to be completely withdrawn from the study, and no more data will be collected from the subject. The study team will no longer access the patient's medical record or other confidential records requiring the subject's consent.

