#### 6. Procedures Involved

[figure not shown]

Figure 1. Application of E-Stim Device

Electrical stimulation will be applied to the quadriceps muscle groups on both lower extremities simultaneously for 30 minutes at a time (Figure 1). The patient will be positioned either supine or sitting.

A Vectra Neo Clinical Therapy System (Chattanooga Group) will be used to provide the stimulation. The stimulator will be set up and taken off the patients by a member of the study team or a trained ICU staff member. The stimulation parameters will be as follows:

Electrode location: Proximal and distal quadriceps

Waveform: pulsed biphasic Pulse duration: 300-450 µseconds Pulse frequency: 35 pulses per second

Amplitude: palpable, visible quadriceps muscle contraction

On/off time: 10 seconds on, 30 seconds off Ramp up and down time: 2 seconds each

Total treatment time:  $45 \pm 15$  minutes/day, for a total of at least 5 treatments each week (Mon-Sun), until ICU discharge or at the

discretion of the research team.

At Neuro ICU discharge, a member of the study team will assess functional recovery using the modified Rankin Scale (mRS) and the Extended Glasgow Outcome Scale (GOSE). (uploaded in eIRB) Subjects who withdraw from e-stim treatment may still be assessed with these instruments at discharge, unless they request to withdraw from data collection as well. Subjects may be withdrawn from e-stim treatment without their consent if their physician or the study team decides that it is in their best interest (e.g. due to skin irritation or burns).

All procedures will be performed as part of the research study, and not as standard of care.

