#### 7. Data

## a. Handling of Data

Data will be collected from the subjects' medical record in Epic, and from the mRS and GOSE instruments (completed by study staff). All data will be stored in REDCap. Data collected from the medical record will include demographics (sex, age, race), illness information (primary admission diagnosis, severity of critical illness as determined by the Sequential Organ Failure Score (SOFA) and/or APACHE II score), critical illness associated complications (e.g. deep vein thrombosis, hospital acquired infection, etc.), and medications associated with neuromuscular weakness (e.g. steroids, neuromuscular blockers, etc.). Data will be stored indefinitely.

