#### **Group Comparisons**

The study team statistician will analyze the data, and will be blinded to treatment assignment ("Group A" and "Group B", instead of "E-Stim Group" "Historical Controls"). Descriptive statistics will be used to quantify feasibility. Mean length of stay and mean duration of intubation will be compared between the e-stim group and the historical controls using a t-test. If necessary, a linear regression model for length of stay and/or intubation duration will be used to compare between groups while controlling for the potential confounding of covariates. A Wilcoxon rank-sum test will be used to compare the exploratory functional outcome measures between groups, as the mRS and GOSE are both ordinal scales.

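### For persistent skin irritation, Section 10 withdraws the subject from the study but Section 6 only from e-stim treatment, so outcomes of a subject who never declined could be lost

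*Combined protocol and SAP*

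**What the plan says.** Two sections deal with the same event in different terms.

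- **Section 10 (Risks and Benefits), item 2.** A subject with skin irritation is first switched to hypoallergenic electrodes. After that: "If the skin irritation persists, the subject will be withdrawn from the study". The rule is mandatory and applies to the study.
- **Section 6 (Procedures Involved).** "Subjects may be withdrawn from e-stim treatment without their consent if their physician or the study team decides", with skin problems as the example: "decides that it is in their best interest (e.g. due to skin irritation or burns". The rule is discretionary and applies to treatment. The sentence before it, on subjects who themselves stop treatment, says they "may still be assessed with these instruments at discharge, unless they request to withdraw from data collection as well".

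Three other places bear on the point.

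- **Section 10, item 3.** For pain, the team "will discontinue the intervention if the subject either reports pain or has signs of pain". It does not mention leaving the study.
- **Section 5f (Consent Process).** A subject who stops e-stim but agrees to a recovery assessment stays enrolled. One who refuses is "completely withdrawn from the study, and no more data will be collected from the subject", and the team stops accessing the medical record.
- **Section 8 (Group Comparisons).** "Mean length of stay and mean duration of intubation will be compared between the e-stim group and the historical controls using a t-test". It does not say whether a subject taken off treatment by the team stays in the e-stim group.

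**The concern.** The protocol treats stopping e-stim while enrolled and leaving the study as different states, and it attaches the end of data collection to the second. Section 10 puts a subject with persistent irritation into the second state by name, although neither the subject nor the LAR has asked to leave. Staff who follow Section 10 literally could stop collecting that subject's outcomes or leave the subject out of the comparison.

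ICU stay, mRS and GOSE are fixed around ICU discharge, so normally after stimulation has stopped. All three would be exposed. Duration of intubation is exposed only if the subject is still intubated when withdrawn.

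Such a loss would not be random dropout. The treatment would cause it, and it could occur only in the e-stim arm, because the control figures are averages abstracted from an existing database (Section 6, Historical Controls). It would also be unnecessary. Section 7a takes the data from the "medical record in Epic, and from the mRS and GOSE instruments (completed by study staff"), and neither source needs stimulation to continue.

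**Working it through.** The plan gives no figure on this point to reproduce. The check is a comparison of the texts, followed by the scale of a possible loss.

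**Texts compared**

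| Place | Trigger | Who decides | What stops | Later data |
|---|---|---|---|---|
| Section 10, item 2 | Irritation persisting after electrode switch | Team (mandatory) | Study participation | Not stated |
| Section 6 | Skin irritation or burns, as examples | Physician or team (discretionary) | E-stim treatment | mRS and GOSE may be assessed; worded for subjects who withdraw themselves |
| Section 10, item 3 | Pain or signs of pain | Team | Intervention | Not stated |
| Section 5f | Subject stops e-stim, agrees to assessment | Subject | E-stim treatment | Continues |
| Section 5f | Subject stops e-stim, refuses assessment | Subject | Study participation | Ends, with record access |

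The first two rows conflict on what stops. The only place that describes what follows from leaving the study is the last row. Its trigger is refusal, so it does not prescribe the same consequence for a withdrawal by the team. No row guarantees that data collection continues after such a withdrawal.

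**Scale of loss.** Inputs: 22 e-stim subjects and 23 historical controls (Section 8, Power Calculation).

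1. Share of the arm per subject lost: 1/22 = 0.0455, or 4.5%.
2. Precision for ICU stay. With equal SDs in the two groups (an assumption), the standard error of the difference is proportional to sqrt(1/n1 + 1/n2).
   - Planned: sqrt(1/22 + 1/23) = 0.2982.
   - One e-stim subject lost: sqrt(1/21 + 1/23) = 0.3018.
   - Ratio: 0.3018/0.2982 = 1.012, an increase of 1.2%.
3. Shift in the e-stim mean. If the lost subject's stay differs by d days from the mean of the other 21, the mean moves by d/22, or 0.045 day per day of difference. As an illustration only, d = 10 gives 10/22 = 0.45 day.

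Items 2 and 3 apply to ICU stay, where all 22 subjects count. Intubation duration covers only those intubated.

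**Chance of any case.** The documents give no rate of persistent irritation. For an assumed rate p per subject, the chance of at least one case in 22 is 1 − (1 − p)^22:

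| Assumed p | Chance of at least one case |
|---|---|
| 1% | 0.20 |
| 2% | 0.36 |
| 5% | 0.68 |
| 10% | 0.90 |

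The range is too wide to say whether a case should be expected. It does not add to the importance of the point.

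**The case against.** The strongest reply is that this is loose wording in a risk section. Section 6 is the operative section. It names the same trigger and limits the consequence to treatment, and its neighbouring sentence keeps discharge assessment open. Read together, those two sentences naturally cover subjects whom staff take off treatment. Item 3 of Section 10 speaks of stopping the intervention, which suggests that item 2 meant no more than that. The Section 5f rule ending data collection follows only from refusal, so a subject withdrawn by the team who has not refused falls outside it. Section 8 excludes nobody from the e-stim group, and its silence on early stopping is general rather than a product of the Section 10 phrase. The trigger is also narrow: adhesive and tape allergy are excluded at entry, and the irritation must survive the electrode switch.

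Most of this stands. Section 6 is the more natural rule to follow, no text prescribes the loss, and the 1.2% figure measures precision rather than the selective loss that is the actual worry. These points keep the matter minor. They do not remove it, because the Section 10 sentence is mandatory, is the more specific about irritation that persists, and is not overridden anywhere. A reader who obeys it as written has no instruction to keep collecting data.

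**Conclusion.** The inconsistency is real and minor. Followed literally, Section 10 permits treatment-caused loss of outcomes, in the e-stim arm only, from subjects who did not decline. That loss is possible, not prescribed.

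The effect is probably small, at the size per lost subject shown above. The standard-error figure rests on equal SDs and on the planned group sizes. The number of subjects affected and the direction of any bias cannot be determined from the documents. Confidence is high that the two sections differ; whether any data would in fact be lost depends on how staff read Section 10.

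**What to change.** In Section 10, item 2, change withdrawal from the study to withdrawal from e-stim treatment, which matches Section 6. Add one sentence: ICU stay, duration of intubation, mRS and GOSE continue to be collected, and are analysed in the e-stim group, unless the subject or LAR declines.

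The cost is one phrase and one sentence. Stimulation still stops under the same rule, so safety is unaffected. The right under Section 5f to refuse data collection is preserved. No visits are added, because the outcomes come from the medical record and the discharge assessment already planned.

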## 11. Resources Available

Not applicable

## 12. Devices

The Vectra® Neo Clinical Therapy System is a modular system that can be used with or without an optional Cart, allowing for the inclusion of Channel 1/2 Electrotherapy module with or without sEMG, Channel 3/4 Electrotherapy module, Laser module and Ultrasound module. The device we will use will be used without the cart and will have the 2 channel electrotherapy module, without sEMG, laser or ultrasound. The system is commercially manufactured by Chattanooga, a subsidiary of DJO in Vista, California. The device is FDA approved for the prevention of disuse atrophy. It is also used for muscle re-education, increasing range of motion and increasing circulation. This device is used in commonly in clinical Physical Therapy practice in other patient populations.

